11.5 Follow up procedures

After initially recording an AE or recording and reporting an SAE, the Investigator is required to follow each participant until resolution. Follow up information on an SAE should be reported to the Study Office.

12. STATISTICS

12.1 The Revised Sample size Calculation

The sample size for the study was determined in order to show that a quantitative assessment of SPCr or SACr at a given cut-off can safely rule out the possibility of severe PE. In diagnostic testing terms, the test should have a LR- of 0.1 or smaller, and a sensitivity of at least 90% with high specificity. Previous studies suggest that SPCr or SACr (when fully quantitative), might achieve this.

To demonstrate with 80% power that sensitivity is at least 90% within 95% confidence limits, assuming that sensitivity is actually 95%, requires 240 women with severe PE.

In an interim analysis of the first 500 recruited women we found 78 who met a proxy definition of severe PE (primary outcome data not yet being available for most participants) – that is, a prevalence of 15.6%. This estimate is likely to be conservatively low, as 81 women (16.2%) out of the first 500 recruited women did not have enough data currently available to determine even the proxy outcome. Allowing for 14% of participants to have missing data on the primary outcome in the final analysis, we therefore need to recruit 1710 women with gestational hypertension and suspected PE to the study. We have based this 14% estimate on the preliminary analysis of the first recruited 1200 women.

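### The recruitment target in section 12.1 does not follow from its inputs: 1710 conflicts with the 14% allowance and with the 1790 in the summary, and the 15.6% prevalence already carries missing-outcome loss

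*Protocol*

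**What the plan says.** Section 12.1 of the Protocol builds the recruitment target in three steps.

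- **Cases.** The aim is put this way: "To demonstrate with 80% power that sensitivity is at least 90% within 95% confidence limits". With a true sensitivity of 95% taken as given, the section sets the requirement at 240 cases.
- **Prevalence.** "In an interim analysis of the first 500 recruited women we found 78 who met a proxy definition of severe PE". The section turns this count into a percentage and comments on it: "that is, a prevalence of 15.6%. This estimate is likely to be conservatively low, as 81 women (16.2%) out of the first 500" recruits lacked the data to settle even the proxy. The section adds that the primary outcome itself was not yet available for most participants at that look.
- **Missing outcomes.** "Allowing for 14% of participants to have missing data on the primary outcome in the final analysis", the section states that 1710 women must be recruited. The 14% is taken from a preliminary analysis of the first 1200 recruits.

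The Protocol Summary (section 4) gives the study size as 1790.

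**The concern.** There are two separate difficulties.

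1. **The target.** Section 12.1 and the summary give different numbers, and the number in section 12.1 does not come out of the inputs stated beside it.
2. **The denominator.** The 81 women who could not be classified are counted in the 500 but cannot contribute to the 78. The 15.6% is therefore identified proxy cases per woman recruited, with the unclassified women treated in effect as non-cases. An allowance for missing outcomes belongs on a prevalence among women whose outcome is known. Applied to 15.6%, it allows for missing outcomes a second time.

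At stake is whether the stated 80% power belongs to the stated target. The two difficulties pull in opposite directions: the first leaves 1710 short of 240 cases, the second makes either target more than 80% power needs. A reader of section 12.1 cannot tell which describes the study.

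**Working it through.** **Inputs (Protocol section 12.1 unless noted).** Sensitivity to exclude 0.90; assumed true sensitivity 0.95; power 80%; 95% confidence limits, read here as two-sided 5% because sidedness is not stated; 240 cases; 78 proxy cases among 500 recruits, 81 unclassified; 14% missing; targets 1710 (section 12.1) and 1790 (section 4).

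**Step 1: the 240 cases.** One-sample proportion:

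n = [(1.960 × √(0.90 × 0.10) + 0.842 × √(0.95 × 0.05)) / 0.05]² = 238.0

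The stated 240 is reproduced; the same approximation gives 80.4% power at 240.

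**Step 2: the plan's route to the target.**

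- 78/500 = 0.156, and 240/0.156 = 1538.5.
- With 14% missing: 1538.5/0.86 = 1788.9, which matches 1790.
- With 10% missing: 1538.5/0.90 = 1709.4, which matches 1710.
- Multiplying by 1.14 instead of dividing by 0.86 gives 1753.8, which matches neither.

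So the stated inputs lead to the summary's figure and not to the one in section 12.1.

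**Step 3: counting missing outcomes once.**

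- Cases per woman recruited, no further allowance: 240/0.156 = 1539.
- Cases per classified woman, then 14% missing: 500 − 81 = 419; 78/419 = 18.6%; 240/(78/419)/0.86 = 1500.
- Consistency check: with 16.2% missing in place of 14%, the second route gives 240/(78/419)/0.838 = 1538.5, the same as the first. That confirms that 15.6% already contains the loss of the 81 women.

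**Step 4: cases and power at each target.** Power ≈ Φ[(0.05 − 1.960 × √(0.09/n)) / √(0.0475/n)], with n the expected number of cases.

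| Reading of the prevalence | Cases at 1710 | Power | Cases at 1790 | Power |
|---|---|---|---|---|
| 15.6% of evaluable women, 14% missing (N × 0.86 × 0.156) | 229 | 78.1% | 240 | 80.4% |
| 15.6% of women recruited (N × 0.156) | 267 | 85.3% | 279 | 87.2% |
| 18.6% of classified women, 14% missing (N × 0.86 × 78/419) | 274 | 86.4% | 287 | 88.2% |

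Exact (Clopper-Pearson) power moves in a sawtooth with n: 77.7% at 240, 83.6% at 279. Averaged over n ± 6 it is 80.0% at 240, 86.3% at 279 and 87.5% at 287. The two methods agree to about one percentage point once the sawtooth is smoothed.

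**The case against.** The strongest defence is that the section discloses the low estimate and names the 81 women as the reason. On that view the surplus is a safety margin, and an input that gives more than 80% power does no harm. This stands in part: nothing is hidden, and the overlap alone does not cost power. But the section does not say that the 14% covers the same kind of loss, does not size the margin, and presents the result as the number required.

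A second defence is that the two kinds of missingness differ. The 81 women lacked data for a proxy at an interim look; the 14% concerns the primary outcome at the final analysis and comes from a different, larger set of women. Some of the 81 may be classified later, and a proxy case may end without a primary outcome. This also stands: 78/500 is not a firm final case yield.

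A reader might go further and infer that the target is simply too high, that recruitment should be cut to about 1500 to 1539, and that months of recruitment are being wasted. The document does not support that. The exact 95% interval for 78/500 is 12.5% to 19.1%; at the lower limit 1790 recruits yield 1790 × 0.125 = 224 cases even when counted per woman recruited. The surplus at 1790 also disappears if only about 84% to 86% of proxy cases prove to be evaluable true cases (240/287; 240/279). Section 12.2 further plans analyses in women with 1+ or more on dipstick, and possibly stratified by assay, which would use fewer cases. Keeping a margin is a reasonable choice; leaving it unstated is the fault.

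Neither defence touches the conflict between 1710, 14% and 1790.

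**Conclusion.** The point holds in two parts.

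- **Certain, by arithmetic alone:** 1710 does not follow from 240 cases, 15.6% and 14% missing. Those inputs give 1789, which agrees with the 1790 in the summary; 1710 corresponds to 10% missing. On the plan's own reading, 1710 is about 11 cases short of 240.
- **Holds, with assumptions:** missing-outcome loss enters both through the denominator of 78/500 and through the 14%. The size of the surplus assumes that the proxy stands in for the primary outcome and, on the 18.6% route, that the unclassified women resemble the classified ones.

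Depending on the reading, the power at 1710 lies anywhere from about 78% to 86%, and at 1790 from about 80% to 88%. The case requirement of 240 is sound under a two-sided 5% reading. This is a fault in how the target is derived and reported, not a threat to the study's validity and not a ground for reducing recruitment.

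**What to change.** Rewrite the last part of section 12.1 so that it:

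1. gives one target, reconciled with the 14% allowance and with the Protocol Summary;
2. names the prevalence denominator and applies missingness once, either 78/500 per woman recruited with no further allowance or 78/419 among classified women with 14% missing; or else says outright that both allowances are kept as a deliberate margin because the prevalence rests on an interim proxy;
3. states the expected number of cases and the power for the target that is kept, for example from the table above.

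If the first 1200 recruits also supply a usable prevalence, it would be a better basis than the first 500; the Protocol says only that the 14% came from them.

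The cost is a text correction in sections 12.1 and 4. No change to recruitment, procedures or data collection follows from it.

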4. PROTOCOL SUMMARY

Short title:	DAPPA
Protocol version:	2.0
Protocol date:	7 th April 2015
Chief Investigator:	[name]
Sponsor:	The Newcastle upon Tyne Hospitals NHS Foundation Trust
Funder:	NIHR Health Technology Assessment programme
Study design:	Prospective cohort study to evaluate the diagnostic accuracy of SPCr and SACr in comparison with 24 hour proteinuria in hypertensive pregnant women with suspected proteinuria. We will also undertake decision analytic modeling and cost effectiveness analysis.
Primary objective:	To evaluate the diagnostic accuracy of quantitative assessments of SPCr and SACr (index tests) at different thresholds in predicting severe PE compared to 24 hour urine protein measurement
Secondary objectives:	
To assess the accuracy of point of care assessments of SPCr and SACr at different thresholds in diagnosing PE compared to 24 hour urine protein measurement
 
To identify the laboratory assay method of 24 hour proteinuria that is most accurate in the assessment of PE
 
To estimate the accuracy of both quantitative and point of care assessments of SPCr and SACr at different thresholds in predicting adverse fetal outcomes
 
To estimate the diagnostic utility of SPCr or SACr as a potential replacement for 24 hour protein estimation by developing a decision analytic model
 
To assess the cost effectiveness using cost per correct diagnosis and cost per adverse outcome predicted as key measures

Primary outcome:	Severe PE as defined by NICE [5]
Number of study sites:	Up to 36
Study population/size:	1790
Study duration:	44 months

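### Section 12.1 sets recruitment at 1710, but its own inputs give 1790, the figure in the protocol summary

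*Protocol*

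**What the plan says.** Section 12.1 of the protocol builds the sample size in three steps.

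- **Cases.** The aim is "To demonstrate with 80% power that sensitivity is at least 90% within 95% confidence limits", "assuming that sensitivity is actually 95"%, and this "requires 240 women with severe PE".
- **Prevalence.** Among the first 500 recruits, 78 met a proxy definition of severe PE: "that is, a prevalence of 15.6"%. The section adds that this is probably an underestimate, because 81 of the 500 could not be classified even on the proxy.
- **Missing outcome.** "Allowing for 14% of participants to have missing data on the primary outcome in the final analysis", a rate taken from the first 1200 women, "we therefore need to recruit 1710 women with gestational hypertension and suspected PE to the study".

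Section 4 (Protocol Summary) of the same version gives a different total: "Study population/size: 1790".

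**The concern.** The recruitment figure in section 12.1 is presented as following from the inputs just before it, yet it differs from the summary by 80 women. One of the two must be wrong. If it is the figure in the statistics section, a team that treats it as the target would stop short of the number of severe PE cases on which the power statement rests. At the planned 70 women per month (sections 7.4 and 9.1.1), 80 women is 80/70 = 1.1 months of recruitment.

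**Working it through.** **Inputs, all from section 12.1:** minimum sensitivity p0 = 0.90; assumed sensitivity p1 = 0.95; 95% confidence limits; power 80%; 240 cases; prevalence 78/500 = 0.156; missing primary outcome 0.14. The section does not say whether the limits are one- or two-sided. I take two-sided, because that reproduces the 240.

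**Step 1: the case number reproduces.** For a one-sample proportion by normal approximation,

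n = [(1.96 × √(p0(1−p0)) + 0.8416 × √(p1(1−p1))) / (p1−p0)]² = [(1.96 × 0.3 + 0.8416 × 0.2179) / 0.05]² = 238.0.

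This rounds up to 239, in line with the stated 240.

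**Step 2: the recruitment number does not reproduce.** N = cases / prevalence / (1 − missing).

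| Missing allowance | Calculation | N |
|---|---|---|
| none | 240/0.156 | 1538.5 |
| 10% | 1538.5/0.90 | 1709.4 |
| **14% (as stated)** | **1538.5/0.86** | **1788.9** |
| 16.2% (81/500) | 1538.5/0.838 | 1835.9 |

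The stated 14% gives 1789, or 1790 rounded, which is the summary's figure. The common but incorrect inflation, 1538.5 × 1.14 = 1754, does not give 1710 either. Only the 10% row does.

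**Step 3: expected cases with 14% missing and 15.6% prevalence.**

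- 1710 × 0.86 × 0.156 = 229.4
- 1790 × 0.86 × 0.156 = 240.1

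The shortfall at 1710 is about 11 cases.

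**Step 4: power, by the formula that reproduces 240.** Power = Φ[(0.05√n − 1.96 × 0.3) / 0.2179].

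- n = 229: 78.0%
- n = 240: 80.4%

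Exact (Clopper-Pearson) power is saw-toothed: 74.2% at 229 and 77.7% at 240. Wilson limits give 82.5% and 77.7% at the same two values, so exact results at a single n should not be over-read. Averaged over neighbouring n, the Clopper-Pearson figures are about 77.5% and 80.0%, the same loss of 2 to 2.5 points.

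**The case against.** The strongest objection is that the shortfall may not be real. The 15.6% counts all 81 unclassified women as non-cases, and section 12.1 warns that it is probably too low for that reason.

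- At 1710 recruits with 14% missing, 240 cases need a prevalence of 240/(1710 × 0.86) = 16.3%. Four cases among the 81 would be enough: 82/500 = 16.4%, giving 241 cases.
- If the unclassified women resemble the others, prevalence is 78/419 = 18.6%. Then 1710 recruits give about 274 cases, with power of about 86%.
- Because the 500 in the denominator already includes women without outcome data, the further 14% inflation may partly count missingness twice. Without it, 1710 × 0.156 = 266.8 cases.

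It can also be said that the power loss is only about 2 points at face value, that the summary already carries the right figure, and that section 7.4 ends recruitment by date rather than by count.

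Most of this stands as a limit on the practical consequence: the study is not shown to be underpowered. In the other direction, the proxy is not defined, so it could also over-count cases relative to the final definition. None of it explains 1710. The protocol chose 15.6% as its planning value, applied 14% on top of it, and nowhere offers the cautious prevalence as a reason to recruit fewer women. The conflict with the summary remains whatever the true prevalence is.

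**Conclusion.** The concern holds. With 240 cases, 15.6% prevalence and 14% missing, the recruitment target is 1789, rounded to 1790. The 1710 in section 12.1 is 80 below the summary's figure and corresponds to a 10% allowance. It may have been left unchanged when the allowance was revised to 14%, but the document does not say so and this is inference.

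On the protocol's own assumptions, 1710 gives about 229 cases and about 78% power. That effect is modest and conditional on the 15.6%. The case for correction rests mainly on a core design number being stated two ways, with the version in the statistics section at odds with its own derivation.

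**What to change.** In section 12.1, replace 1710 with 1790, so that the total follows from the 14% allowance and agrees with section 4. Showing the chain 240/0.156/0.86 in the text would let a reader check it.

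If 1710 is the intended target, change section 4 to match and state in section 12.1 that, at 15.6% prevalence and 14% missing, it gives about 229 expected cases and about 78% power.

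The first option costs one number in the protocol and changes nothing for sites already working to 1790.

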12.2 Analysis

We aim to show that a quantitative assessment of SPCr or SACr can safely rule out the possibility of adverse outcomes. Diagnostic accuracy of laboratory and POC care measurements of SPCr and SACr at given cut-offs will be summarised using sensitivity, specificity, and positive and negative likelihood ratios, estimated using standard methods for proportions. Sensitivity and specificity at different cut-offs will be used to plot non-parametric receiver operating characteristic (ROC) curves for the different assays. Laboratory quantitative assessments of SPCr and SACr, POC are assays, and laboratory measures of 24-hour urine protein will be compared by looking at the difference between the areas under the respective ROC curves. Caution should be exercised if an ROC curve is used to select an “optimal” cut-off for a continuous test measure without validation in a separate sample. We will use our sample to validate cut-offs identified in previous research [7]. By restricting analyses to those women with 1+ or higher on the automated dipstick test, we will evaluate test performance in the population of women who would currently be referred for further testing. Because we may wish to consider making testing more inclusive, we will also analyse our entire sample to evaluate test performance in women with trace or higher on the automated dipstick test.

In addition we will use linear regression to explore the relationship between each SPCr/SACr measurement and the local measurement of 24-hour proteinuria (“linear” regression in the sense of a Normal model with linear link function; we will have a large enough sample to investigate non-linear associations between SPCr/SACr and 24-hour proteinuria). In particular, we will investigate whether the relationship is different at sites using different 24-hour assays, and whether these differences might be explained by measured patient characteristics. If there are differences between sites, our primary analysis of diagnostic accuracy will be stratified by the type of 24-hour assay used. To make use of the full sample, and to try and obtain more generalizable results, we will also fit multivariable logistic regression models for predicting outcomes using SPCr/SACr, site, and patient characteristics.

All analyses will be carried out using Stata v11 (Stata Corporation, College Station, Texas USA).

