6. AIMS OF THE STUDY

Our proposed study evaluates the measurement of proteinuria in women with suspected preeclampsia (PE). This includes women with gestational hypertension $\geq 140/90$ mmHg and \geq Trace proteinuria on automated dipstick analysis.

Primary Objectives:

1. To evaluate the diagnostic accuracy of quantitative assessments of SPCr and SACr (index tests) at different thresholds in predicting severe PE compared to 24 hour urine protein measurement

Secondary Objectives:

2. To assess the accuracy of point of care assessments of SPCr and SACr at different thresholds in diagnosing PE compared to 24 hour urine protein measurement
3. To identify the laboratory assay method of 24 hour proteinuria that is most accurate in the assessment of PE
4. To estimate the accuracy of both quantitative and point of care assessments of SPCr and SACr at different thresholds in predicting adverse fetal outcomes
5. To estimate the diagnostic utility of SPCr or SACr as a potential replacement for 24 hour protein estimation by developing a decision analytic model
6. To assess the cost effectiveness using cost per correct diagnosis and cost per adverse outcome predicted as key measures

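### The only statistical comparison of accuracy between tests in Section 12.2 is whole ROC area, which does not determine performance at the high sensitivity that rule-out needs

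*Protocol*

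**What the plan says.** Protocol Section 12.1 sets the target for a test that can exclude severe PE: "the test should have a LR- of 0.1 or smaller, and a sensitivity of at least 90% with high specificity". It sizes the study on sensitivity alone: "To demonstrate with 80% power that sensitivity is at least 90% within 95% confidence limits". Section 12.2 opens with the same purpose: "We aim to show that a quantitative assessment of SPCr or SACr can safely rule out the possibility of adverse outcomes".

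The primary objective in Section 6 is comparative and tied to thresholds. SPCr and SACr are to be evaluated "at different thresholds in predicting severe PE compared to 24 hour urine protein measurement".

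Section 12.2 then plans two things for accuracy:

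- Test by test: each index test, at chosen cut-offs, has its results "summarised using sensitivity, specificity, and positive and negative likelihood ratios, estimated using standard methods for proportions". The sentence names SPCr and SACr but not 24-hour protein.
- Between tests: the laboratory ratios, the point-of-care assays and "laboratory measures of 24-hour urine protein will be compared by looking at the difference between the areas under the respective ROC curves".

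The linear regression that follows relates SPCr and SACr values to 24-hour values. It does not compare accuracy for severe PE.

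**The concern.** A rule-out test is used at a cut-off where few cases are missed, so what matters is how many non-cases it clears at that point. Total AUC averages specificity over every sensitivity from 0 to 100%, including the range that no rule-out test would use. Two tests with equal areas can differ widely in specificity at 95% sensitivity. Two tests that perform alike at that point can differ in area.

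The comparative half of the primary objective therefore rests on a measure that does not isolate the property defined in Section 12.1. A reader of the results could see similar areas for an index test and 24-hour protein and learn little about how they compare where it matters.

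**Working it through.** **1. The plan's own figure.** Inputs from Section 12.1: null sensitivity 90%, true sensitivity 95%, 80% power, 95% confidence limits.

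n = [(1.960 × √(0.90 × 0.10) + 0.842 × √(0.95 × 0.05)) / 0.05]² = 238.03, so 239. The protocol states 240, which is reproduced. The study is thus sized at a high-sensitivity operating point, one test at a time. With the stated prevalence of 15.6%, 240 cases imply 240 / 0.156 − 240 = 1298 non-cases.

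**2. How much of the area concerns rule-out.** AUC is specificity averaged over sensitivity from 0 to 1. The band from 0.90 to 1.00 can add at most 0.10. At an AUC of 0.85, at least (0.85 − 0.10) / 0.85 = 88% of the area comes from sensitivities below 90%. This needs no assumption about curve shape.

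**3. Equal area, different rule-out value.** The protocol gives no AUCs or curve shapes, so binormal curves are assumed, with b = SD of non-cases / SD of cases.

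- a = Φ⁻¹(AUC) × √(1 + b²)
- specificity at 95% sensitivity = 1 − Φ((1.645 − a) / b)
- LR- = 0.05 / specificity

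For AUC 0.85, Φ⁻¹(0.85) = 1.036:

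| b | a | Specificity at 95% sensitivity | LR- |
|---|---|---|---|
| 0.5 (case SD twice the non-case SD) | 1.159 | 16.5% | 0.302 |
| 0.7 | 1.265 | 29.4% | 0.170 |
| 1 | 1.466 | 42.9% | 0.117 |
| 1.5 | 1.868 | 55.9% | 0.089 |

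The area difference is zero in every row, yet LR- falls on both sides of the 0.1 limit. Two tests with the same b would give the same row, and then area and rule-out value agree.

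**4. Equal rule-out point, different area.** Fix sensitivity 95% and specificity 50%, so LR- = 0.05 / 0.50 = 0.10. Then a = 1.645 for any b, and AUC = Φ(1.645 / √(1 + b²)). This is 0.878 for b = 1 and 0.819 for b = 1.5, a difference of 0.058.

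With 240 cases and 1298 non-cases, the Hanley–McNeil standard error at AUC 0.85 is 0.0160. If r is the correlation between the two area estimates (assumed), the standard error of the difference is 0.0160 × √(2(1 − r)). Multiplying by 2.80 gives the difference detectable with 80% power: 0.064 for r = 0, 0.045 for r = 0.5 and 0.028 for r = 0.8. A gap of 0.058 would usually stand out for r of 0.5 or more.

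**5. What a rule-out contrast could see.** Paired binormal tests were simulated with 240 cases and 1298 non-cases. Assumptions: AUC 0.75 or 0.85, case SD of one test 1.25 to 2 times that of the other, within-class correlation 0.5 or 0.8. With equal areas, a paired area test rejected 3–9% of the time. A paired test of specificity at 95% sensitivity rejected 13–39% for an 8-point gap, 46–91% for 14–15 points and 83–100% for 21–26 points. Large gaps are detectable and small ones often are not.

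**The case against.** The strongest reply is that the protocol already answers the rule-out question without the area comparison.

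- Section 12.1 frames rule-out test by test, and Section 12.2 reports sensitivity, specificity and LR- at cut-offs and plots the curves. An LR- of 0.12 or 0.30 for an index test would be seen. This stands, but no contrast with 24-hour protein at a cut-off is stated.
- Replacement is assigned elsewhere. The objective that speaks of a "potential replacement for 24 hour protein estimation" says this will be judged through a decision analytic model. Section 12.3 lists dipstick plus 24-hour protein as one of the options, works from true and false positives and negatives, and uses 24-hour protein as the comparator for the ICER. This also stands.
- A reader might infer that a non-significant area difference would pass a worse test as a fair replacement, or that a significant one would reject an equally good test. The protocol does not support this. It names no formal test, significance level, margin or decision for the area difference, and does not call that comparison primary.
- A reader might also take the result in step 4 as an inflated false-positive rate. It is not: the true areas differ there, so detecting the difference is power for a different question.
- Specificity at 95% sensitivity does not suit every assay. The semi-quantitative SACr strip in Section 8.1 reports three ranges, hence two operating points, and generally has no 95% sensitivity cut-off. Section 12.2 also warns against choosing cut-offs in the same sample. Both points stand and shape the fix.

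Paired contrasts could also appear in an analysis plan not shown here. But the protocol is not silent on the metric. It names whole area, and the point concerns that choice.

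**Conclusion.** The concern holds in a limited form. Section 12.2 fixes whole ROC area as its only statistical comparison of accuracy between the index tests and 24-hour protein, and that measure does not determine performance at high sensitivity. At a common AUC of 0.85, specificity at 95% sensitivity is 43% or 17% (LR- 0.12 or 0.30) when case SD equals or is twice the non-case SD.

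These sizes rest on assumed binormal curves and spread ratios. With similar shapes the disagreement disappears, and the documents do not say which situation applies. Because test-by-test LR- and the decision model cover part of the question, and nothing in the protocol makes the area difference decisive, this is a worthwhile, inexpensive improvement. It does not make the analysis invalid.

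**What to change.** In Section 12.2:

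- Make the main between-test comparison the paired difference in sensitivity, specificity and LR- between each index test and 24-hour protein at pre-specified cut-offs, each with a 95% CI. Name the cut-offs for every test, 24-hour protein included. This form also works for the semi-quantitative strip.
- For the continuous assays, add the paired difference in specificity at a fixed sensitivity (for example 95%). Take the 95% CI from a bootstrap that resamples women and re-estimates the cut-off in each sample. Present it as a contrast between tests, so that it does not become a way of choosing a cut-off.
- Keep the difference in full area as a supportive summary.

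The cost is a paragraph of text and a bootstrap on data already being collected. The statistical price is a wider interval than for the full area, since with 240 cases the 95% sensitivity cut-off rests on about 0.05 × 240 = 12 missed cases. The change does not alter the fact that proteinuria is part of the severe PE definition in Section 7.1, which can affect any comparison with 24-hour protein whichever measure is used.
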